As niclosamide was approved by FDA to treat tapeworms in humans, it has a well-understood clinical safety profile on oral administration at 2000 mg daily for up to 7 days. In addition, it has been studied in clinical trials in oncology and several other indications, and two other Sponsors have recently initiated trials of niclosamide in COVID-19 patients. This Investigational New Drug Application represents the first clinical use of ANA001 capsules, thus there is no previous clinical data to report for this formulation of niclosamide.

[figure not shown]
3.1. Study Rationale

ANA001 is a new formulation containing 250 mg niclosamide per capsule. Although other niclosamide formulations have been studied for tapeworm infections and other potential human uses, limited systemic PK/PD data exists in the literature. To ensure proper systemic levels of niclosamide are achieved for therapeutic effect, a SAD/MAD study with ANA001 capsules is necessary.

3.2.1. Chemical Name/Structure

USAN: Niclosamide

IUPAC: 5-Chloro-N-(2-chloro-4-nitrophenyl)-2-hydroxybenzamid

Molecular formula: C₁₃H₈Cl₂N₂O₄

Molecular weight: 327.1 g/mol

Oral toxicology studies for NDA 018669 evaluated niclosamide in mice, rats, rabbits, dogs, and cats. Single dose studies included doses as high as 5000 mg/kg in rats without any lethality (reviewed in [Andrews et al., 1982](#)). A repeat dose study with dogs showed that single oral doses of 6000 mg/kg for 8 consecutive days, followed by 4500 mg/kg for another 24 consecutive days were tolerated well with no signs of intoxication (reviewed in [Andrews et al., 1982](#)). Other repeat dose studies in rabbits, cats or dogs with doses that were 2-5 times the human therapeutic dose and lasted 11, 12, and 84-96 days were non toxic, based on routine laboratory tests and toxicology. Male cats were noted to have a mild reduction in white blood cells (WBC), and dogs showed a tendency toward watery stools, but otherwise adverse treatment effects were not evident. Other studies reported that doses of 250 mg/kg may cause vomiting in dogs and cats. The conclusion of these studies was that niclosamide was a low risk for dosing orally in humans at the standard therapeutic regimen of 2000 mg/day (BAYER NDA 018669; Summary Basis for Approval (SBA)).

3.2.3. Safety

Between 1971 and 1978, niclosamide was administered to 6365 patients under a US IND. Doses were up to and including 2000 mg/day for 7 days. There were 2385 evaluable patients, of which 13.3% reported side effects, all of which were mild or moderate, with none requiring treatment discontinuation. These included nausea/emesis in 4.1%, abdominal discomfort/loss of appetite in 3.4%, diarrhea in 1.6%, drowsiness/dizziness/headache in 1.4%, and skin rash/pruritis in 0.3% of patients (NDA 018669 Review Documentation).

In addition, according to the Safety Review of Niclosamide, Pyrantel, Triclabendazole and Oxamniquine report of the World Health Organization (WHO), there have been 84 reported adverse drug reactions related to niclosamide between 1975 and 2004 in the WHO database. They include 173 reports from 16 countries and the most common reactions are related to skin and appendages (41 reports), gastrointestinal tract (37 reports), cardiovascular system (28 reports) and anaphylactic reactions (9 reports).

Niclosamide was approved as a pregnancy class B drug and is thus safe to use during pregnancy.

Summarized below are safety assessment findings reported in the available literature:

- Prostate cancer patients received 500 mg and 1000 mg of niclosamide orally thrice per day for 15 days. TID regimens of >500 mg PO per day suggested the potential for DLT, however these findings are confounded by coadministration of antineoplastic treatment associated with a similar range of GI disturbances and occurred after niclosamide was dosed for >7 days ([Schweizer et al., 2018](#)).
- Colorectal cancer patients received 2000 mg of niclosamide orally once per day until disease progression or toxicity (up to four months). No adverse side effects were reported ([Burock et al., 2020](#)).

- 2000 mg niclosamide/person did not result in hematological changes ([Andrews et al., 1982](#)).
- No induction of methemoglobinemia was observed in men after oral administration of 30 mg/kg b.w. (~2000 mg/person) ([Andrews et al., 1982](#)).
- Men and women received 1000 mg niclosamide once or twice per person; children (6-15 years of age) received 750-1000 mg/person; neither scenario resulted in signs of intoxication ([Andrews et al., 1982](#)).
- In a Phase I study, adults were divided into two groups (niclosamide and placebo). Study participants received 2000 mg/day for 3 days with a repeat course 6 days later. Transitory reactions, such as loose stools and stomach aches were reported ([Andrews et al., 1982](#)).
- No dermal sensitizing effect was observed upon topical administration ([Andrews et al., 1982](#)).

At the established doses, most adverse events were transitory and generally mild to moderate.

3.3. Benefit/Risk Assessment

Niclosamide is approved for dosing up to 2000 mg PO daily for 7 days. There is limited safety and PK data in humans receiving more than 2000 mg as a single dose and/or more frequently than once daily. The current SAD/MAD study is designed to explore the safety and PK of dosing up to 3000 mg/day as a single dose and regimens not to exceed 2000 mg/day as divided doses BID or TID. In light of the immediate pressing need for development of an effective and safe oral therapeutic that can prevent progression of COVID-19, the benefit to risk ratio for the study is anticipated to be justified.

More detailed information about the known and expected benefits and risks and reasonably expected adverse events of ANA001 may be found in the Investigator's Brochure.

4. Objectives and Endpoints

Objectives	Endpoints
Primary	
• To assess safety and tolerability of single oral daily doses of ANA001 (1000 mg, 2000 mg and 3000 mg)• To assess safety and tolerability of multiple daily oral doses (twice daily [BID] or thrice daily [TID]) of ANA001 for 7 days
Secondary	
• Incidence of adverse events (AEs), serious AEs (SAEs), study drug discontinuation due to an AE (MAD portion only), use of concomitant medications, and change from baseline in clinical laboratory tests, vital signs, electrocardiograms (ECG), and physical examinations
	
• To assess the PK of single and multiple doses of ANA001• AUC_{0-t}, AUC_{0-last}, $AUC_{0-\infty}$ (SAD only), C_{max}, t_{max}, $t_{1/2}$, CL/F, V_z/F

5. Study Design

5.1. Overall Design

This is a randomized, double-blind study to be conducted in two parts: single ascending dose (SAD) and multiple ascending dose (MAD). Potential participants for each part will undergo screening procedures within 30 days of enrolment.

SAD

On Day -1, eligible participants will be randomly assigned to active drug or placebo in an 8:2 ratio. On Day 1, following an overnight fast of at least 10 hours, participants will receive their assigned treatment (1000 mg, 2000 mg, or 3000 mg of ANA001) with a standardized light meal (500 to 750 cal). A baseline ECG will be performed at Screening and at 3 hours after dosing. Blood pressure and heart rate will be measured every 8 hours while confined to the clinic. Blood for PK will be collected before dosing and at 0.5, 1, 2, 4, 6, 8, 10, 12 and 24 hours after dosing. Participants will be discharged on Day 2 following the 24-hour PK sample and completion of clinical laboratory tests and physical examination. They will return on Day 7 (± 2) for follow-up procedures including physical examination, laboratory tests, and assessment of AEs and concomitant medication use.

MAD

On Day -1, eligible participants will be randomly assigned to active drug or placebo in a 9:3 ratio on a BID (q12h) or TID (q8h) schedule, to be determined based on the PK results of the SAD cohorts. Total daily doses will not exceed 2000 mg of ANA001. On Days 1 through 7, participants will receive their assigned treatment in the morning with a standardized light meal (500 to 750 cal) following an overnight fast of at least 10 hours. Afternoon or evening doses will be given with a light snack. A baseline ECG will be performed at Screening and at 3 hours after the second dose on Day 7. Blood pressure and heart rate will be measured every 8 hours while confined to the clinic.

During BID dosing, blood for PK will be collected on Days 1 and 7 before dosing and at 0.5, 1, 2, 4, 6, 8, 10, and 12 hours after dosing. Blood samples will also be collected on Days 2, 4, 6, and 8 before dosing and before the 12 hour dose on Days 2, 4, and 6.

During TID dosing, blood for PK will be collected on Days 1 and 7 before dosing and at 0.5, 1, 2, 4, 6, and 8 hours after dosing. Blood samples will also be collected on Days 2, 4, 6, and 8 before dosing, before the 8 hour dose on Days 2, 4, and 6, and before the 16 hour dose on Day 6.

Participants will be discharged on Day 8 following the last PK sample and completion of clinical laboratory tests and physical examination. They will return on Day 15 (± 2) for follow-up procedures including physical examination, laboratory tests, and assessment of AEs and concomitant medication use.

5.2. Participant and Study Completion

A minimum of 30 participants will be enrolled in the SAD part and up to 36 participants in the MAD part. At least 3 participants of each sex will be included in each cohort.

5.3. End of Study Definition

A participant is considered to have completed the study if he/she has completed all phases of the study including the last scheduled procedure shown in the Schedule of Activities.

The end of the study is defined as the date of the last visit of the last participant in the study.

5.4. Scientific Rationale for Study Design

Sequential timing of the ascending dose cohorts will allow early stopping if serious or unanticipated safety signals are observed at any dose level.

6.1. Inclusion Criteria

Participants are eligible to be included in the study only if all of the following criteria apply:

1. Signed the COVID and study informed consent forms as described in [Appendix 3](#) which includes compliance with the requirements and restrictions listed in the informed consent form (ICF) and in this protocol
2. Man or woman, 18 to 65 years of age inclusive at the time of signing the informed consent form
3. Overtly healthy as determined by medical evaluation including medical history, physical examination, clinical laboratory tests
4. Body mass index (BMI) within 18 to 30.0 kg/m² (inclusive) and body weight not less than 50 kg
5. Blood pressure (after supine for 5 minutes) at Screening and Day -1 between 90 and 140 mmHg systolic, inclusive, and no higher than 90 mmHg diastolic.
6. A 12-lead electrocardiogram (ECG) at Screening consistent with normal cardiac conduction and function, including:
 - Sinus rhythm
 - Pulse rate between 50 and 100 beats per minute (bpm)
 - QTc interval 450 milliseconds (QT interval corrected using Fridericia correction method [QTcF])
 - QRS interval of <120 milliseconds
 - PR interval <200 milliseconds
 - Morphology consistent with healthy cardiac conduction and function
7. Non-smoker or ex-smoker for >12 months
8. If male, must agree to use contraception as detailed in [Appendix 5](#) of this protocol during the treatment period and for at least 30 days (a spermatogenesis cycle) after the last dose of study treatment and refrain from donating sperm during this period
9. If female, is not pregnant (see Appendix 5), not breastfeeding, and meets at least one of the following conditions:

Not a woman of childbearing potential (WOCBP) as defined in Appendix 5

OR

A WOCBP who agrees to follow the contraceptive guidance in Appendix 5 during the treatment period and for at least 30 days (one menstrual cycle) after the last dose of study treatment.

Note: Retesting of abnormal laboratory values that may lead to exclusion will be allowed once. Retesting will take place during an unscheduled visit in the screening phase.

6.2. Exclusion Criteria

Participants are excluded from the study if any of the following criteria apply:

1. Has a history of or current clinically significant medical illness including but not limited to: cardiac arrhythmias or other cardiac disease; hematologic disease; coagulation disorders (including any abnormal bleeding or blood dyscrasias); lipid abnormalities; significant pulmonary disease, including bronchospastic respiratory disease; diabetes mellitus; hepatic or renal insufficiency (creatinine clearance below 60 mL/min); thyroid disease; neurologic or psychiatric disease; infection; or any other illness that the Investigator considers should exclude the subject or that could interfere with the interpretation of the study results.
2. Has known allergy to niclosamide or salicylate-containing medications.
3. Clinically significant abnormal values for hematology, clinical chemistry, or urinalysis at screening as assessed per [Appendix 6](#)
4. Clinically significant abnormal physical examination, vital signs or 12 lead ECG at screening as deemed appropriate by the Investigator
5. Has a history of human immunodeficiency virus (HIV) antibody positive, or tests positive for HIV; has a history of hepatitis B surface antigen (HBsAg) or hepatitis C antibody (anti-HCV) positive, or other clinically active liver disease, or tests positive for HBsAg or anti-HCV at Screening.
6. History of drug or alcohol abuse according to Diagnostic and Statistical Manual of Mental Disorders (4th edition) criteria within 5 years before screening or positive test result(s) for alcohol and/or drugs of abuse at screening and admission
7. Has received an investigational drug or used an invasive investigational medical device within 1 month or within a period less than 10 times the drug's half-life, whichever is longer, before Day 1.
8. Has preplanned surgery or procedures that would interfere with the conduct of the study
9. Is an employee of the Investigator or study site, with direct involvement in the proposed study or other studies under the direction of that Investigator or study site, as well as family members of the employees or the Investigator

6.3. Lifestyle Restrictions

6.3.1. Meals and Dietary Restrictions

1. Participants will refrain from consumption of red wine, Seville oranges, grapefruit or grapefruit juice, pomelos, exotic citrus fruits, grapefruit hybrids, or fruit juices from 3 days before the start of study treatment until after the final dose.

6.3.2. Caffeine, Alcohol, and Tobacco

1. Participants will abstain from ingesting caffeine- or xanthine-containing products (e.g., coffee, tea, cola drinks, and chocolate) for 24 hours before the start of dosing until after collection of the final pharmacokinetic (PK) blood sample.
2. Participants will abstain from alcohol for 24 hours before the start of dosing until after collection of the final PK blood sample.
3. Use of tobacco products will not be allowed during the study.

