6.3.3. Activity

1. Participants will abstain from strenuous exercise for 24 hours before each blood collection for clinical laboratory tests. Participants may participate in light recreational activities during studies (e.g., watching television, reading).

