7.7. Concomitant Therapy

Any medication or vaccine (including over-the-counter or prescription medicines, vitamins, and/or herbal supplements) that the participant is receiving at the time of enrollment or receives during the study must be recorded along with:

- Reason for use
- Dates of administration including start and end dates
- Dosage information including dose and frequency

The Medical Monitor should be contacted if there are any questions regarding concomitant or prior therapy.

Participants must abstain from taking prescription or nonprescription drugs (including vitamins and dietary or herbal supplements) within 7 days (or 14 days if the drug is a potential enzyme inducer) or 5 half-lives (whichever is longer) before the start of study treatment until completion of the follow-up visit, unless, in the opinion of the Investigator and Sponsor, the medication will not interfere with the study.

Acetaminophen, at doses of \leq 2 grams/day, is permitted for use any time during the study. Other concomitant medication may be considered on a case-by-case basis by the Investigator.

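### The alcohol restriction ends at the last PK sample, 3 to 9 days before the follow-up safety visit, and drinking in between is neither limited nor recorded

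*Protocol*

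**What the plan says.** Protocol section 6.3.2, item 2 sets the alcohol rule: "Participants will abstain from alcohol for 24 hours before the start of dosing until after collection of the final PK blood sample". Section 6.3.1 also restricts red wine, but that rule ends sooner, after the final dose.

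Section 5.1 fixes the dates.

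- **SAD:** "Participants will be discharged on Day 2 following the 24-hour PK sample and completion of clinical laboratory tests and physical examination". Then: "They will return on Day 7 (± 2) for follow-up procedures including physical examination, laboratory tests, and assessment of AEs".
- **MAD:** "Participants will be discharged on Day 8 following the last PK sample and completion of clinical laboratory tests and physical examination". Then: "They will return on Day 15 (± 2) for follow-up procedures including physical examination, laboratory tests, and assessment of AEs".

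Three other restrictions do cover the follow-up visit.

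- **Exercise (6.3.3):** "Participants will abstain from strenuous exercise for 24 hours before each blood collection for clinical laboratory tests".
- **Other drugs and supplements (7.7):** barred from a set interval "before the start of study treatment until completion of the follow-up visit", with exemptions by investigator and sponsor judgement and an allowance for acetaminophen.
- **Tobacco (6.3.2, item 3):** not allowed during the study.

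The Schedules of Activities place the urine alcohol screen at Screening and Day -1 only. They list no alcohol assessment after that.

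**The concern.** Safety is the primary objective, yet the alcohol rule is tied to PK sampling. Participants leave the clinic with no limit on drinking and return days later for chemistry (including AST, ALT, alkaline phosphatase and bilirubin, per Appendix 2), hematology and AE assessment. Section 3.2.3 lists nausea/emesis and drowsiness/dizziness/headache among the side effects reported for niclosamide. I assume, without a figure from the documents, that drinking can produce similar symptoms and can move liver tests. If so, a follow-up finding could come from either cause, and the data collected would not help to tell them apart. At stake is how to read isolated findings in the one laboratory set that looks for delayed effects.

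**Working it through.** The plan states no figure to reproduce here: Protocol section 10.1 says the sample size has no statistical basis. The check covers dates, data flow and one illustration.

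**1. Length of the unrestricted interval.** Gap = follow-up day (nominal ± 2) minus day of the final PK sample, all from section 5.1.

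- SAD: 5 − 2 = 3; 7 − 2 = 5; 9 − 2 = 7. Gap 3 to 7 days, nominally 5.
- MAD: 13 − 8 = 5; 15 − 8 = 7; 17 − 8 = 9. Gap 5 to 9 days, nominally 7.

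**2. Laboratory sets affected.** From the Schedules of Activities, post-dose chemistry and hematology are drawn on Days 2 and 7 (SAD) and Days 2, 5, 8 and 15 (MAD). The follow-up set is 1 of 2 in SAD and 1 of 4 in MAD. The other sets are drawn in the clinic, at or before the end of the restriction.

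**3. Route into the primary endpoint.** SAP section 2.2.1 counts change from baseline by visit and treatment-emergent laboratory abnormality as primary outcomes. SAP section 8.2 allows shift tables against reference ranges, where a value only mildly above normal shows as high. Protocol section 9.2.1 collects AEs until the follow-up visit. In SAP section 8.1 the treatment-period condition attaches to the worsening of pre-existing events. I read new events as treatment-emergent with no end date, so those arising after discharge count.

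**4. The comparison value.** SAP section 5.2 defines baseline as the last value before dosing. For chemistry and hematology that is the Day -1 draw. The restriction begins 24 hours before dosing, so this draw falls at or near its start, after days of normal living.

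**5. How far placebo helps.** Let p be the rate of a non-drug finding at follow-up, from any cause. It is not in the documents; I assume 2% to 10%. The chance of at least one such finding on active and none on placebo is

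P = [1 − (1 − p)^(n active)] × (1 − p)^(n placebo).

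For example, SAD pooled (24 active, 6 placebo) at p = 5%: (1 − 0.95^24) × 0.95^6 = 0.708 × 0.735 = 0.520.

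| Group (active : placebo) | p = 2% | p = 5% | p = 10% |
|---|---|---|---|
| One SAD cohort (8:2) | 14.3% | 30.4% | 46.1% |
| SAD pooled (24:6) | 34.0% | 52.0% | 48.9% |
| One MAD cohort (9:3) | 15.6% | 31.7% | 44.7% |
| MAD pooled (27:9) | 35.1% | 47.2% | 36.5% |
| MAD pooled (30:6) | 40.3% | 57.7% | 50.9% |

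The last row is there because Protocol section 5.1 gives a 9:3 MAD ratio, while the Protocol synopsis and SAP section 3 give 10:2 in their design text and 9:3 in their cohort lists. Those passages need reconciling, but the point here does not depend on it. Under these assumptions, a pattern that looks like a drug effect arises by chance often enough that a clean placebo group would not settle the cause of an isolated finding.

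**The case against.** The best defence is that the trial already limits the damage.

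- **Both arms are treated alike.** A reader might infer that the gap biases active against placebo. It does not: the study is randomized and double-blind under one rule. This objection stands in full.
- **Baseline is not an alcohol-free inpatient value.** A reader might infer that follow-up values are set against an alcohol-restricted stay. The endpoint is change from the Day -1 draw, so both ends of the contrast are close to outpatient conditions. This also stands, and it affects the remedy. Counted from Day 1, abstinence through to follow-up would mean about 4 to 8 alcohol-free days in SAD (5 − 1 to 9 − 1) and 12 to 16 in MAD (13 − 1 to 17 − 1), against about 24 hours or less before baseline. That could make the two draws less alike.
- **Laboratory AEs have a high bar.** A reader might infer that drinking would inflate laboratory TEAE counts. Appendix 6 asks for AST or ALT above 3 times ULN or a rise over 200%, and total bilirubin above 2.5 times ULN or a rise over 150%. Nothing in the documents shows that drinking by screened healthy adults would reach those limits. Smaller shifts would touch the change-from-baseline summaries and shift tables only.
- **Attribution is addressed.** Appendix 4 makes the investigator weigh alternative causes, SAP section 8.1 tabulates TEAEs by relationship, Protocol section 9.1.4 requires repeat testing, and section 6.2 excludes alcohol abuse within 5 years. This stands in part. The causality review has no scheduled alcohol information after Day -1, and a repeat test shows that a value has resolved, not what caused it.
- **The comparators are loose.** The exercise rule covers only 24 hours, the drug rule has exemptions, and caffeine shares the PK end point. So the documents do not show that abstinence to follow-up was intended. They also give no reason why alcohol should be handled differently from exercise before a safety draw.

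**Conclusion.** The gap is real and small in consequence. For 3 to 7 days (SAD) or 5 to 9 days (MAD) before the follow-up visit, drinking is neither restricted nor recorded. It can therefore add non-drug noise to the only scheduled post-discharge laboratory set and to post-discharge TEAEs. The in-clinic laboratory sets are unaffected.

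The size of the effect cannot be stated, because the documents give no alcohol effect and no drinking rate. One event is 12.5 points among 8 active participants, 11.1 among 9 and 50 among 2 placebo. A reader might take these as the harm, but they hold for any single event from any cause and say nothing about alcohol. The placebo illustration rests on assumed rates of 2% to 10% and shows only that attribution is weak in groups of this size.

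This is a design gap, not a contradiction or a wrong figure. It merits a cheap improvement and does not threaten the trial's conclusions.

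**What to change.** Extend Protocol section 6.3.2, item 2 so that alcohol is also barred for a stated period before the follow-up laboratory draw. The period should be at least the 24 hours that section 6.3.3 uses for exercise, and chosen so that the follow-up draw is taken under conditions comparable to the Day -1 baseline draw. At the follow-up visit, record alcohol intake since discharge, so that the causality assessment in Appendix 4 has something to work from.

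If the sponsor prefers abstinence through the whole follow-up period, the restriction before baseline should be lengthened to match.

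The cost is a sentence in the protocol and the consent form, a short extra restriction for participants, and one CRF question at a visit that already takes place. Outpatient abstinence would be self-reported, since no alcohol screen is scheduled at follow-up. Dosing, stopping rules and the planned analyses do not change.
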